#### 5.2.8 **Supportive Care Guidelines for Study Treatment Toxicity**

200 mg QD, Days 1-7, q3w

Toxicity will be managed by the investigator according to the local standard of care. Supportive treatment must be reported in the concomitant medication section of the eCRF.

Handling of hepatotoxicity for potential DILI will be managed according to the treatment guidelines outlined in Appendix 5.

### **5.2.9** Potential Phototoxicity

No phototoxicity studies have been performed in humans to date. However as OTX015/MK-8628 absorbs light in the range of 290 and 400 nm with a molar extinction coefficient (MEC) of >1000 L/mol.cm, it is recommended that patients avoid sun and UV exposure until results of phototoxicity studies are available.

#### **5.3** Treatment Duration

Patients will continue study treatment until any of the following events at which point it will be definitively discontinued:

- Disease progression
- Unacceptable toxicity
- Patient withdrawal of consent
- Patient non-compliance
- Treatment interruption for > 2 weeks for any reason (except in the event of perceived benefit, with Sponsor agreement)
- Recurrence of DLT despite dose reduction (except in the event of perceived benefit, with Sponsor agreement)
- Any of the following liver test abnormalities\*\* (see Appendix 5)
  - ALT or AST > 8 x ULN
  - ALT or AST > 5 x ULN for > 2 weeks
  - ALT or AST > 3 x ULN and (total bilirubin > 2 x ULN OR INR > 1.5)
  - ALT or AST > 3 x ULN with the appearance of fatigue, nausea, vomiting, right upper quadrant pain or tenderness, fever, rash and/or eosinophilia (> 5%)

However, in case of investigator's perceived benefit for the patient, treatment continuation can be considered with dose reduction despite delay/interruption > 2 weeks or reoccurrence of a DLT with the same intensity after one dose reduction. The perceived benefit of the investigator is defined by 1) any objective tumor response, or 2) any tumor shrinkage not meeting standard response criteria, but which could improve with additional treatment, or 3) any symptomatic improvement, which, in the investigator's opinion, could not be achieved by other means. If, in the cases described above, DLT recurs with the same intensity despite one dose reduction, a second dose reduction may be considered. The decision should be discussed with the Sponsor, but the final decision must be made by the investigator.

[figure not shown]
In all cases, the reason for and date of study treatment discontinuation must be recorded in the eCRF and source documented in the patient's medical records. As far as possible, there should be only one reason for treatment discontinuation. If there are several (e.g. concomitant progressive disease and toxicity), the primary one must be reported. The patient must be followed up to establish whether the reason was a TEAE, and if so, this must be reported as such.

As far as possible, all examinations scheduled for the final study day must be performed for all patients who receive the investigational product but who do not complete the study according to protocol.

The investigator must make every effort to contact patients lost to follow-up, especially when a patient is treated in another non-study center.

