## Non-hematologic toxicity

- Any grade 3 or 4 non-hematologic toxicity (regardless of duration) unless it was not optimally managed with supportive care (e.g. grade 3 vomiting not adequately treated according to antiemetic standard of care).
- Any grade 3 or 4 laboratory abnormality, with or without symptoms, lasting > 48 hours.
- Any intolerable grade 2 non-hematologic toxicity resulting in study drug discontinuation or delay > 7 days with or without dose reduction.

No more than two dose reductions (or schedule modifications) should be implemented, unless the investigator thinks it in the patient's best interests to pursue study treatment with a further dose reduction (an additional dose level), with the Sponsor's agreement.

Dose / Schedule Modifications: Regimen 1					
Initial OTX015 Dose	1st Modification	2 nd Modification			
80 mg QD continuously	80 mg QD, 2 weeks ON/ 1 week OFF, q3w	60 mg QD, 2 weeks ON/1 week OFF, q3w			
100 mg QD continuously	100 mg QD, 2 weeks ON/1 week OFF, q3w	80 mg QD, 2 weeks ON/1 week OFF, q3w			
120 mg QD continuously	120 mg QD, 2 weeks ON/1 week OFF, q3w	100 mg QD, 2 weeks ON/1 week OFF, q3w			
160 mg QD continuously	160 mg QD, 2 weeks ON/1 week OFF, q3w	120 mg QD, 2 weeks ON/1 week OFF, q3w			

Dose / Schedule Modifications: Regimen 2											
Initial OTX015 Dose	1st Modification	2 nd Modification									
100 mg QD, Days 1-7, q3w	80 QD, Days 1-7, q3w	60 QD, Days 1-7, q3w									
120 mg QD, Days 1-7, q3w	100 mg QD, Days 1-7, q3w	80 QD, Days 1-7, q3w									
160 mg QD, Days 1-7, q3w	120 mg QD, Days 1-7, q3w	100 mg QD, Days 1-7, q3w									
200 mg QD, Days 1-7, q3w	160 QD, Days 1-7 q3w	120 mg QD, Days 1-7, q3w									

Dosing interruption for > 2 weeks due to toxicity or liver toxicity (see treatment duration for details) will lead to definitive study treatment discontinuation unless the investigator thinks it is in the patient's best interests to pursue study treatment, with the Sponsor's agreement.

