#### 3 STUDY DESIGN, DURATION AND DATES

#### 3.1 Study Design

This is an open-label, multicentric, international, non-randomized phase I trial with dose optimization of single-agent OTX015/MK-8628 administered *per os* in patients with selected advanced tumors (NMC, TNBC, NSCLC, CRPC and PDAC).

The study will be performed in two parts. In the first part a dose escalation study will be performed evaluating two regimens in parallel to establish the MTD in each of the selected indications. In the second part, the efficacy of OTX015/MK-8628 will be evaluated in expansion cohorts of each of the five indications using a selected regimen. Patients will be included in at least seven centers worldwide.

The two regimens evaluated in parallel in the dose escalation part are:

Regimen 1: continuous, once daily for 21 consecutive days (21-day cycles), at a starting dose of 80 mg/day.

Regimen 2: once daily on days 1 to 7, repeated every 3 weeks (21-day cycles; 1 week ON/2 weeks OFF), at a starting dose of 100 mg/day.

A sequential accrual design with standard dose escalation is used. Patients will be included in the next available regimen.

Up to four dose levels will be evaluated for each regimen.

Regimen 1: 80, 100, 120 and 160 mg/day, continuous, 21-day cycles

Regimen 2: 100, 120, 160 and 200 mg/day, 1 week ON/2 weeks OFF, 21-day cycles

Patients will undergo a dose and/or schedule modification in the event of toxicity.

Three patients will be enrolled per dose level, and up to three additional patients at the first occurrence of a DLT (see Section 5.2.4) during the first 21 days of treatment. Up to 48 patients evaluable for DLT will be enrolled in the dose escalation part (24 for each regimen).

The MTD will be the dose level at which fewer than one-third of the patients experience DLT during the first 21 days, and is defined as the DL at which 0 out of 3 patients or 1 out of 6 patients experiences DLT, with the next higher DL having at least 2 out of 3 to 6 patients having DLT.

Once the MTD is established for each regimen and at least 3 patients have received at least two evaluable cycles of study drug at the MTD, an expansion step will be initiated to assess the efficacy of OTX015/MK-

8628 in these populations, as measured by clinical benefit (CR, PR or SD, according to RECIST v1.1 or PCWG2). Up to 50 evaluable patients (10 per indication) will be accrued in the expansion phase.

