# Non-hematologic toxicity

- Any grade 3 or 4 non-hematologic toxicity (regardless of duration) unless it was not optimally managed with supportive care (e.g. grade 3 vomiting not adequately treated according to antiemetic standard of care).
- Any grade 3 or 4 laboratory abnormality, with or without symptoms, lasting > 48 hours.
- Any intolerable grade 2 non-hematologic toxicity resulting in study drug discontinuation or delay > 7 days with or without dose reduction.

After recovery from toxicity, the dose will be resumed as follows and detailed in Table 11:

- For Regimen 1, the continuous schedule will be initially modified to a discontinuous schedule, then with a dose reduction for the second modification.
- For Regimen 2, two consecutive dose reductions may be implemented.

Dose / Schedule Modifications: Regimen 1 2nd Modification **Initial OTX015 Dose** 1st Modification 80 mg QD continuously 80 mg QD, 60 mg QD, 2 weeks ON/1 week OFF, q3w 2 weeks ON/1 week OFF, q3w 100 mg QD continuously 100 mg QD, 80 mg OD. 2 weeks ON/1 week OFF, q3w 2 weeks ON/1 week OFF, q3w 120 mg QD continuously 120 mg QD, 100 mg QD, 2 weeks ON/1 week OFF, q3w 2 weeks ON/1 week OFF, q3w 160 mg QD continuously 120 mg OD, 160 mg OD, 2 weeks ON/1 week OFF, q3w 2 weeks ON/1 week OFF, q3w

Table 11: OTX015/MK-8628 Dose / Schedule Modifications

Dose / Schedule Modifications: Regimen 2 **Initial OTX015 Dose** 1st Modification 2nd Modification 100 mg QD, Days 1-7, q3w 80 QD, Days 1-7, q3w 60 QD, Days 1-7, q3w 120 mg QD, Days 1-7, q3w 80 QD, Days 1-7, q3w 100 mg QD, Days 1-7, q3w 160 mg QD, Days 1-7, q3w 120 mg QD, Days 1-7, q3w 100 mg QD, Days 1-7, q3w

No more than two dose reductions (or schedule modifications) should be implemented unless the investigator thinks it in the patient's best interests to pursue study treatment with further dose reduction (additional dose reduction by one dose level), with the Sponsor's agreement.

120 mg QD, Days 1-7, q3w

160 QD, Days 1-7 q3w

Dosing interruption for > 2 weeks due to toxicity or liver toxicity (see Section 5.3 for details) will lead to definitive study treatment discontinuation, unless the investigator thinks it in the patient's best interests to pursue study treatment, with the Sponsor's agreement.

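### Sections 5.2.7 and 5.3 give incompatible instructions for a Regimen 2 patient whose toxicity recurs after one dose reduction without perceived benefit, and 5.3 leaves open what counts as a dose reduction or a recurrent DLT

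*Protocol*

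**What the plan says.** Protocol 5.2.7 and Table 11, repeated in the synopsis under Treatment Adaptation, set out a first and a second modification for every dose level once toxicity has resolved. The order differs by regimen. For the continuous regimen: "For Regimen 1, the continuous schedule will be initially modified to a discontinuous schedule, then with a dose reduction for the second modification". For the intermittent regimen: "For Regimen 2, two consecutive dose reductions may be implemented". Neither step carries a benefit condition. The cap comes next: "No more than two dose reductions (or schedule modifications) should be implemented unless the investigator thinks it in the patient's best interests". Going beyond it also needs the Sponsor's agreement.

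Protocol 5.3, repeated in the synopsis under Duration of Treatment, lists the events that end treatment for good. One is: "Recurrence of DLT despite dose reduction (except in the event of perceived benefit, with Sponsor agreement"). Section 5.3 then defines perceived benefit as an objective response, shrinkage short of a formal response, or symptomatic improvement not obtainable otherwise. Within those cases it continues: "If, in the cases described above, DLT recurs with the same intensity despite one dose reduction, a second dose reduction may be considered".

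Protocol 5.2.4 confines DLT to the first 21 days of treatment.

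**The concern.** Both sections speak to the patient whose dose has been lowered once and whose toxicity has come back. One makes a second reduction available as an ordinary step. The other makes stopping the default and the second reduction an exception. Section 5.2.7 refers to 5.3 only for interruptions longer than two weeks and for liver toxicity, so nothing in the text says which section governs a recurrence.

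The term that triggers 5.3 is a second difficulty. The cap in 5.2.7 counts dose reductions and schedule modifications together, whereas 5.3 speaks only of dose reduction. Because Regimen 1 begins with a schedule change, the point at which 5.3 takes effect there depends on a definition that the protocol does not give.

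At stake is, first, that investigators handling recurrent severe toxicity read the same instruction. Second, discontinuations and dose adaptations due to AEs are secondary safety endpoints (Protocol 11.2, SAP 2.4) presented by dose level and regimen (Protocol 11.4, SAP 2.6). A site following 5.2.7 would record a dose adaptation where a site following 5.3 would record a discontinuation.

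**Working it through.** The plan states no dose-intensity figure, so there is nothing to reproduce. The check places the rules side by side and then computes where 5.3 first applies.

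**Side by side.** Take a Regimen 2 patient with stable disease, no shrinkage and no symptomatic change, whose toxicity returns at the same intensity after the first reduction.
- Under 5.2.7 and Table 11, a second reduction is available and no further approval is needed.
- Under 5.3, a dose reduction has been made, the toxicity has recurred, and none of the three perceived-benefit conditions is met. Treatment ends.

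Both Regimen 2 steps lower the daily dose, so this holds however *dose reduction* is read. Stable disease counts as clinical benefit in the efficacy endpoint (Protocol 11.2) but is not by itself perceived benefit under 5.3.

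**Where the 5.3 rule first applies.** Starting doses are from Protocol 3.1: "Regimen 1: 80, 100, 120 and 160 mg/day, continuous, 21-day cycles" and "Regimen 2: 100, 120, 160 and 200 mg/day, 1 week ON/2 weeks OFF, 21-day cycles". Modified doses are from Table 11 and its synopsis copy; for example, the second step from 80 mg continuous is "60 mg QD, 2 weeks ON/1 week OFF, q3w".

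Formula: share of starting cycle dose = (modified daily dose × dosing days) / (starting daily dose × starting dosing days). Dosing days are 21 for Regimen 1 at the start, 14 for Regimen 1 after modification, and 7 for Regimen 2 throughout.

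| Regimen, starting dose | After 1st modification | After 2nd modification |
|---|---|---|
| 1, 80 mg (1680 mg/cycle) | 80×14 = 1120, 66.7% | 60×14 = 840, 50.0% |
| 1, 100 mg (2100) | 100×14 = 1400, 66.7% | 80×14 = 1120, 53.3% |
| 1, 120 mg (2520) | 120×14 = 1680, 66.7% | 100×14 = 1400, 55.6% |
| 1, 160 mg (3360) | 160×14 = 2240, 66.7% | 120×14 = 1680, 50.0% |
| 2, 100 mg (700) | 80×7 = 560, 80.0% | 60×7 = 420, 60.0% |
| 2, 120 mg (840) | 100×7 = 700, 83.3% | 80×7 = 560, 66.7% |
| 2, 160 mg (1120) | 120×7 = 840, 75.0% | 100×7 = 700, 62.5% |
| 2, 200 mg (1400) | 160×7 = 1120, 80.0% | 120×7 = 840, 60.0% |

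- *A schedule change is not a dose reduction.* In Regimen 1 the rule first applies after the second modification, at 50.0-55.6%. Both steps in 5.2.7 have then been used, so the sections agree on the count. In Regimen 2 it applies after the first modification, at 75.0-83.3%. The gap at matched dose levels is 19 to 30 percentage points (75.0 − 55.6 = 19.4; 80.0 − 50.0 = 30.0).
- *A schedule change counts.* In Regimen 1 the rule applies after the first modification, at 66.7%, and the conflict found in Regimen 2 appears there too. The gap narrows to 8 to 17 points (75.0 − 66.7 = 8.3; 83.3 − 66.7 = 16.6, or 16.7 unrounded).

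On the first reading, the *daily* dose at the trigger is 75-83% of the starting daily dose in both regimens (Regimen 1: 60/80, 80/100, 100/120, 120/160). The 19-30 point gap is therefore a matter of dose per cycle.

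**Meaning of a recurrent DLT.** With a 21-day DLT window, and dosing resumed only after recovery, a recurrence after a modification will usually fall outside the protocol's definition. Taken literally, the 5.3 criterion would seldom apply. Taken as recurrence of a DLT-type toxicity, it applies throughout treatment and meets 5.2.7 directly, because the 5.2.7 triggers repeat the hematologic DLT criteria and all the non-hematologic ones except the liver tests.

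**The case against.** The best defence is that 5.2.7 grants permission up to a ceiling, while 5.3 is the specific rule for a recurrence. The second step in Table 11 would keep a use, for instance for a different toxicity. Section 5.3 also leaves the final decision to the investigator. This narrows the conflict to a same-intensity recurrence without perceived benefit but does not remove it. Section 5.2.7 allows a choice that 5.3 withdraws, no text ranks the two, and the investigator's final say is written for the perceived-benefit cases.

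A reader might infer more than the documents support:
- *That the sections conflict in both regimens and also apply at very different dose intensities.* These need opposite readings of *dose reduction* for Regimen 1. The larger gap arises only where the sections agree for Regimen 1; if the conflict extends to Regimen 1, the gap is the smaller one.
- *That a Regimen 1 patient with recurrence after the schedule change is covered by no rule.* Section 5.2.7 still interrupts dosing and then lowers the dose, and unacceptable toxicity ends treatment in either regimen.
- *That the committee's choice of regimen is distorted.* Protocol 1.4.2 bases that choice on tolerability, pharmacokinetics and activity, the allocation is not randomized, and nothing shows an effect of this wording. Clinical benefit is a best-response measure, not time on treatment. The SAP (2.2) describes part 2 as a BID regimen, with no choice between Regimens 1 and 2 by indication.

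**Conclusion.** The point stands as an internal inconsistency. For Regimen 2, the two sections, each with its synopsis counterpart, cannot both be followed when a toxicity recurs at the same intensity after one reduction and no benefit is perceived. This rests on reading DLT in 5.3 as DLT-type toxicity at any time, which is the reading that gives the criterion practical use. For Regimen 1, whether the sections conflict depends on an undefined term: the 5.3 rule first applies at 50-56% of starting cycle dose without conflict, or at 67% with it, against 75-83% in Regimen 2 on either reading.

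The consequences are inconsistent patient management and ambiguous counts of discontinuations and dose adaptations due to AEs. How many patients are affected cannot be derived from the documents. The cycle-1 DLT endpoint and the sample size are untouched, and no distortion of regimen selection is shown. It should be corrected, but it does not threaten the primary objective.

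**What to change.** Reconcile four places: 5.2.7 with Table 11, 5.3, and the synopsis text on Treatment Adaptation and on Duration of Treatment.
1. State one rule for what follows a recurrence after a modification, including any benefit condition, and have each section refer to it.
2. Say in 5.3 whether a schedule modification counts as a dose reduction.
3. Say what recurrence of a DLT means after cycle 1.

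Which rule applies is for the sponsor to decide. Simply copying the combined term from the 5.2.7 cap into the 5.3 trigger would not be neutral. It would make recurrence after a schedule change alone a reason to stop in Regimen 1 unless benefit is perceived.

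The cost is amendment wording only, with no added procedures.

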# 5.4 Treatment Assignment

All patients must be registered prior to treatment start. After verifying that the patient meets eligibility criteria and has signed the Informed Consent Form, the investigator will request a patient number by faxing/e-mailing the Patient's Registration Form to:

The Patient's Registration Form (provided separately) contains the following information necessary to determine eligibility:

- 1 Institution name
- 2 Sender's name
- 3. Principal investigator's name
- 4. Patient's identification (first letter of first, middle and last name)
- 5. Patient's age and gender
- 6. ECOG performance status
- 7. Planned date of treatment
- 8. Date when informed consent was obtained
- 9. Verification of selected inclusion and exclusion criteria including hematologic and biochemistry results and dates examinations were performed
- 10. Prior anticancer therapies and dates of last therapies
- 11. Comorbidities and tumor-related symptoms present at screening

After validation and signature by the CRO's Medical Monitor, the registration form will be returned to the investigator, with or without inclusion agreement.

For patients not included, the reason for inclusion refusal will be specified.

For included patients, the dose level and regimen allocated will be specified on the form, along with a unique patient number (UPN). Included patients will receive a UPN only when treatment is about to be started, which must be within 7 days after registration.

The UPN will consist of 5 digits (2 for the center and 3 for the patient, by increasing order of inclusion) and will be recorded on the eCRF. The next consecutive number will be assigned. Once a number has been assigned, it must not be used again.

#### 5.5 Packaging and Labeling

The investigational product OTX015/MK-8628 is manufactured by Agere Pharmaceuticals, Inc. or Merck Sharp & Dohme Limited and packaged by Packaging Coordinators, Inc. It will be supplied as size 3 gelatin capsules containing 10 or 20 mg of OTX015/MK-8628 or size 0 gelatin capsules containing 40 mg OTX015/MK-8628, in bottles of 21 capsules. Clinical supplies will be affixed with a clinical label in accordance with regulatory requirements.

# 5.6 Supplies and Accountability

The pharmacist of the investigational center will inventory and acknowledge receipt of all shipments of the investigational medicinal product which must be kept in a locked area with restricted access. It must be stored and handled in accordance with the manufacturer's instructions and temperature traceability is required.

At each study visit, the hospital pharmacist will provide patients with the adequate number of OTX015/MK-8628 capsules to ensure continuous study treatment until the next visit. The study drug must be used only as directed in the protocol and must be dispensed only to patients enrolled in this study.

The pharmacist will also keep accurate records of the quantities of the investigational product dispensed, used, and returned by each patient. The Sponsor's study monitor will periodically check the supplies of investigational product held by the pharmacist to verify accountability of all investigational product used. The Sponsor will verify that a final report of drug accountability to the unit dose level is prepared and maintained in the Pharmacy Study File. At the conclusion of the study, all unused investigational product and all medication containers will be destroyed by the pharmacist after final accountability by the study monitor and drug accountability has been reviewed and reconciled by the Sponsor and the Sponsor has authorized destruction or return. A certificate of destruction will be provided by the pharmacist to the Sponsor. Alternatively, study medication may be returned to the clinical supply distributor after notification to OTD and OncoEthix. All delivery records must be reconciled with usage records and destroyed or returned. It is essential that all study drugs be accounted for by the site's pharmacist, and that discrepancies are explained and documented.

Complete instructions and contact information for ordering clinical supplies will be supplied in the Investigator File.

### 5.7 Compliance

Administration of the investigational product will be supervised by the investigator. Any delegation of this responsibility must follow Section 12.2.

In practice, on study visit days study nurses will supervise the intake of the appropriate OTX01/MK-86285 dose, explaining to patients the exact number of capsules they should take. Nurses will document in the eCRF the administration, the dose, the time of administration, as well as any immediate reactions at the time of intake.

For non-visit days, OTX015/MK-8628 will be taken at home. The patient will note the number of capsules taken, the time of administration, as well as any reactions including the date/time in a specific patient's diary.

When a patient attends a study visit, he/she will bring any unused capsules and their diary. According to the center procedures, the diary will be used to complete the eCRF treatment administration section, either directly as a Source Document or as an aid for completing the nurse's notes which will be used as a Source Document.

